The study will also determine whether successful treatment of PTSD symptoms improves the cardiac biomarkers proposed to underlie the excess CHD risk in PTSD.

Overview of the Study Approach. The proposed randomized controlled trial (RCT) uses an evidence-based intervention, CPT-C ([name] & Schnicke, 1992), as a tool to induce greater change in PTSD symptom severity compared to WP-CON. The use of a RCT design strengthens our results by controlling and quantifying variability and reducing potential confounding due to selection bias and will enable us to carry out our main goal which is to examine whether changes in PTSD symptom severity impact changes in CHD risk biomarkers. One hundred and twenty men

Figure 1. Pathophysiological Pathway to CHD in PTSD

and women (40-65 years of age) with current PTSD will be randomly assigned in a 2:1 ratio to receive CPT-C or to participate in a waiting period control (WP-CON) condition with minimal attention; CHD biomarkers will be evaluated at baseline and again after completion of CPT-C or after the WP-CON period (see Figure 2). Randomization will be stratified by variables known to be related to both PTSD and to CHD outcomes (gender, age [dichotomization point: 50 years], and comorbid Major Depressive disorder). During the treatment or waitlist phase of the study, PTSD symptoms will be measured every two weeks in each study arm in order to assess changes therein. The WP-CON group will receive minimal attention in the form of weekly telephone calls to assess current emotional state and to provide supportive, nondirective, brief counseling if participants report experiencing a crisis. All prerandomization baseline and post-intervention assessments of PTSD symptoms, psychosocial measures, health behaviors, and CHD biomarkers will be performed by assessors who are blinded to participants' randomization condition.

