General Analytic Strategies. We will examine all variables to determine if parametric distributional assumptions are valid (e.g., normality for the continuous variables). Variables not meeting approximate distributional assumptions will either be transformed or modeled using nonparametric methods. In addition, we will explore the variability and correlation structure of the CHD outcome variables and PTSD symptom severity. Evidence of imbalance in baseline demographic (age, gender, veteran/civilian status) or clinical (high blood pressure, diabetes, major depression) characteristics will be noted and discussed as to whether they are clinically significant and we will consider sensitivity analyses including these covariates in models (models described below separately for each aim), as recommended by the Committee for Proprietary Medicinal Products guidelines (Committee for Proprietary Medicinal Products, 2004). We will also minimize the imbalance on variables known to be related to the predictor and outcome variables by stratifying randomization by gender, age, and major depressive disorder. As the main goal of the aims for this study is to understand how changes in PTSD symptom severity impact changes in CHD markers, we will conduct both an intent-to-treat analysis where participants will be analyzed as part of the group to which they are randomized, regardless of intervention adherence, and a per-protocol or as-treated analysis to strengthen the evidence that the mechanism for the effects of CPT-C vs. control on CHD markers is through PTSD symptom severity changes.

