stratification variables of gender, age, and comorbid major depressive disorder (Committee for Proprietary Medicinal Products, 2004) and as identified in the detailed description of methodologies and in the general analytic section, sensitivity analysis will also include the potential important covariates of functional comorbidity, smoking status, substance abuse, and habitual physical activity. Our main analysis technique for the primary outcome, general linear models via maximum likelihood estimation, uses all available data on subjects, rather than using only subjects with completely observed information, implicitly accommodating missingess when related to prior outcome, or to other baseline covariates included in the model (defined as missing at random).

Aim 2: To examine mechanisms of change in CHD risk biomarker outcomes in a mediation framework. It has been repeatedly demonstrated that individuals suffering from PTSD show excessive SNS, reduced PNS activity, chronic inflammation, and endothelial dysfunction and a number of studies have presented evidence suggestive of the possibility that these CHD markers of risk may be normalized following PTSD treatment (Cohen et al., 2000; Nishith et al., 2003; Blanchard et al.2002; Rabe et al., 2006; Hinton, Hofmann, Pollack, & Otto, 2009). The objective of this aim is to examine whether the change in PTSD symptoms explains the change in CHD biomarkers observed following CPT-C. To achieve this objective, we will test the working hypothesis that improvements in CHD risk biomarkers will be mediated by reductions in PTSD symptom severity. These findings will help establish whether PTSD symptoms themselves are determinants of CHD risk, independently of psychiatric comorbidity and health behaviors associated with cardiovascular risk. When the proposed studies for aim #2 have been completed, it is our expectation that the magnitude of the contribution of PTSD symptom load towards each of the evaluated CHD risk biomarkers will be clarified. Such a finding would be of importance, because it would provide support for a direct role of PTSD symptoms in the CHD risk observed in PTSD and would also identify which cardiac biomarker would provide the most utility in screening and CHD risk stratification in order to predict and prevent the onset of CHD.

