treatment group: $C = \gamma_0 + \gamma_1^*$ treatment. We then fit a model examining the relationship between the mediator and post-treatment change in CHD biomarkers (Y): Y = β_0 + treatment* β_1 + C* β_2 . Finally, to show mediation, we will test that the product of γ_1 and β_2 is not equal to 0 using an extension of the Sobel first-order test (Fritz & MacKinnon, 2007); that is, the the effects of CPT-C on CHD risk biomarkers are attributable to its effects on PTSD symptom improvement. To fully understand these relationships, we will also investigate the MacArthur approach, where our second model will be (Y): Y = β_0 + treatment* β_1 + C* β_2 + C* treatment * β_3 . Under this approach, improvements in CHD biomarkers are attributable to improvements in PTSD symptoms if there is evidence that γ_1 is not equal to 0, and either β_2 or β_3 are not equal to zero. The model will also be adjusted for stratification variables of gender, age, and major depressive disorder, and as detailed above in the general analytic section in the sensitivity analysis, we will evaluate and include other potentially important covariates, including change in anxiety and depressive symptoms estimated from the changes in HADS anxiety and depression following the intervention. We will also explore an as-treated analysis to maximize the potential mediation effects of PTSD symptom severity changes over time. For these analyses, data will be deemed usable for any individual who drops out of the study after two weeks or more of CPT-C or WP-CON, if PTSD symptom change is available and a repeat CHD biomarker assessment can be performed after the PTSD symptom change is assessed.

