Analytic strategy. We will examine whether the effect of PTSD symptom severity changes on change in CHD risk biomarkers is moderated by patient characteristics of gender and major depressive disorder using the summary measure of PTSD symptom severity change that we defined in AIM 2 and the evaluating the outcome of the participants' post-treatment change in CHD risk biomarkers. We will fit a linear model including the predictors: PTSD symptom severity change, and the PTSD symptom severity change arm by moderator variable interaction (gender of major depressive disorder status) with the addition of covariates for baseline demographic and clinical characteristics. We will estimate 95% confidence intervals from these models for the difference in changes in CHD risk markers for PTSD symptom severity level changes by gender and depression status. As outlined in the section describing more detailed methodologies (C.4), the proposed design will also allow us to explore the role of a number of other patient characteristics as potential moderators of the association between change in PTSD symptom severity and change in CHD risk biomarkers (clinical anxiety disorder, socioeconomic status, and social support).

Potential Difficulties/Alternative Approaches. We anticipate that some participants will drop out of trauma focused therapy (CPT-C). In randomized clinical trials of CPT, drop-out rates have been 20-25% ([name], Nishith, Weaver, Astin, & Feuer, 2002; Chard, 2005). However, this is not likely to compromise our analytic approach for the following reasons: (i) we have structured our compensation system so that financial compensation is contingent upon completion of the PTSD and CHD biomarker

assessment, and not contingent upon completion of the full CPT-C treatment or control arm, and we will encourage participants who cease therapy to remain in the study to complete follow-up assessments; (ii) our analytic approach incorporates methods that are robust to incomplete data. In our recent study examining cardiovascular health risk biomarkers among younger adults with and without PTSD that included multiple laboratory sessions and measurement of 24-hour HRV our attrition rates were less than 10%.

B. METHODS

Participants

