
plan to share any incidental findings with participants. Please note that these procedures are optional to participants. Any participant can refuse to participate in genetic testing and still be allowed to participate in the other portions of the study. There are no limitations on the participants' rights to withdraw from the research, withdraw data, or withdraw genetic material. All participants will be provided with an address to which they should send any requests for withdrawal of data or genetic material.

Interventions

Waiting Period Control (WP-CON). The WP-CON group will receive minimal attention in the form of weekly telephone calls to assess current emotional state and to provide supportive, nondirective, brief counseling if participants report experiencing a crisis. Any participant assigned to the WP-CON group will be given the opportunity to receive CPT-C after the post-waiting period assessment. Clients who call in distress during the 6 week control period will be offered the same supportive counseling, and if desired, they will be offered immediate therapy and be referred by [name] and will no longer be included in the study.

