possible lost wages associated with commitment to the study. Participants will be paid up to \$1155 for completion of all aspects of the study. In order to encourage study retention, a staggered reimbursement schedule will be used. Participants will therefore receive \$85 for completing the screening session and \$100 for completion of the baseline assessment, \$100 for completing the inhome urine collection and Holter monitoring,), \$130 for completion of the second session, , and an additional \$200 for completion of the second urine collection and Holter monitoring. Participants in the CPT condition are paid a total of \$45 for completing symptom measures at the therapy sessions, and participants in the waitlist control condition are paid \$45 for completing six telephone calls to assess PTSD symptoms during the waitlist period. Any participant who was assigned to the waitlist group will be offered participation in 12 sessions of CPT and additional monitoring, and therefore may make an additional \$375 [\$130 for office assessment, \$200 for urine collection and Holter monitoring, and \$45 for completion of questionnaires at each CPT session]. Participants can also earn up to \$120 for referring other participants to the study. Participants will be provided parking passes and/or bus passes to encourage attendance at all sessions.

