0.50	40	0.55	22.0
0.50	50	0.55	27.5
0.60	40	0.50	20.0
0.60	50	0.50	25.0

assumed a range of correlations between 0.3 and 0.6 and standard deviations (SD) of 40 and 50. **Table 2** presents effect size differences with 120 subjects. Using the most conservative assumptions, with 80% power, alpha=0.05, SD=50, rho=0.3, and 20% attrition rate by 7-weeks we can detect an effect size difference of 0.60 (Cohen, 1988), corresponding to a difference of 30 units in mean HRV levels at 7-weeks between CPT-C and control. For the AIM 2 mediation analysis, we will test that the effect of CPT-

C on CHD biomarkers is attributable to changes in PTSD severity. We determined detectable effect sizes for mediation based on empirical power estimates for the product-of-coefficient test (i.e., the product of γ_1 and β_2) given by Fritz and MacKinnon (2007). With 120 subjects and a type-I error of 0.05, we will have 80% power to detect medium to large effect size differences for each of the parameters individually (e.g, γ_1 and β_2) that are part of the product test.

Missing Data. Our plans for preventing and dealing with missing data follow the guidelines set forth by the National Research Council's Panel on Handling Missing Data in Clinical Trials. First, , we have numerous strategies in place to prevent attrition; based on prior experience with a similar design and population, we anticipate that we will have less than 20% attrition. Second, as recommended by the panel, we will conduct two general types of sensitivity analyses for our primary analysis. If the missing values are related to measured factors, such as treatment group or baseline comorbidities, then multiple imputation will be used to incorporate information for these auxiliary variables while still preserving a parsimonious main treatment effect model (Collins, Schafer, & Kam, 2001). As a first sensitivity analysis, we will construct a general, multivariate imputation model using all observed CHD markers, treatment group, and any covariates predictive of missingness (Olsen, Stechuchak, Edinger, Ulmer, & Woolson, 2012). The primary analysis models will then be fit to the multiply imputed data and the estimates and standard errors will be combined using appropriate combining rules. We acknowledge the possibility that data may be missing not at random and propose as a second sensitivity analysis to explore pattern-mixture models and the toolkit of methods recently advocated by O'Kelly and Ratitch (2014).

References

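### Waiting-period controls who call in distress and want therapy leave the study, so the control arm alone loses week-7 outcomes, and the rule is not reconciled with the retention and intent-to-treat text

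*Combined protocol and SAP*

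**What the plan says.** All references are to the combined protocol and SAP.

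- **Interventions, Waiting Period Control (WP-CON).** Controls who call in distress during the six weeks get supportive counselling and, "if desired, they will be offered immediate therapy and be referred by [name] and will no longer be included in the study". All controls are offered CPT-C after their post-waiting assessment.
- **General Analytic Strategies.** The plan includes an "intent-to-treat analysis where participants will be analyzed as part of the group to which they are randomized, regardless of intervention adherence", plus a per-protocol or as-treated analysis.
- **Aim 1, Analytic strategy.** The primary model is fitted by maximum likelihood to all available data, "implicitly accommodating missingess when related to prior outcome, or to other baseline covariates included in the model". It contains SDNN at weeks 0 and 7, time, arm by time, gender, age and baseline major depression.
- **Aim 2, Analytic strategy.** Data from people who drop out after at least two weeks in either arm are usable "if PTSD symptom change is available and a repeat CHD biomarker assessment can be performed after the PTSD symptom change is assessed".
- **Potential Difficulties/Alternative Approaches.** Payment follows the assessments and is "not contingent upon completion of the full CPT-C treatment or control arm, and we will encourage participants who cease therapy to remain" in the study for follow-up.
- **Overview of the Study Approach.** "PTSD symptoms will be measured every two weeks in each study arm in order to assess changes therein". Subject Reimbursement also pays controls for "completing six telephone calls to assess PTSD symptoms during the waitlist period".
- **Missing Data.** The first sensitivity analysis is multiple imputation "using all observed CHD markers, treatment group, and any covariates predictive of missingness". The second explores pattern-mixture models.

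**The concern.** The rule creates an exit route in one arm only, and that arm is half the size of the other. What triggers it is distress during the waiting period, a state close to the PTSD symptoms that Aim 2 treats as the mediator. If these people differ at week 7 from the controls who stay, in a way that baseline SDNN and the stratification factors do not explain, the observed control mean is off and the CPT-C contrast moves with it.

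All CHD biomarkers share the same two-time-point design, so one missed T2 visit can cost the primary outcome, the secondary outcomes and a mediator-outcome pair for Aim 2. The text also leaves staff without a clear instruction. One site member could stop all assessments on reading the intervention section, and another could still invite the person to T2 on reading the retention section. Both would be following the protocol.

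**Working it through.** **1. Is the rule specific to one arm?** Yes. There is no matching distress rule for CPT-C. The other exit rule, for acute suicidality (Suicidal and/or Homicidal Ideation), covers both arms.

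**2. The passages side by side.**

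- *Against General Analytic Strategies.* If ending inclusion means only that participation stops, the baseline record stays in WP-CON and nothing is contradicted. If it also meant leaving the analysis, it would contradict intent-to-treat. The sentence does not say which.
- *Against Potential Difficulties.* Payment there does not depend on completing the control arm, which points towards retention. The encouragement to stay names people who cease therapy, so a control who leaves in order to start therapy is not clearly covered.
- *Against Aim 2.* That section expects some WP-CON dropouts to be reassessed where this is possible. The exit rule, followed as written, provides no such assessment.
- *Against Aim 1.* The missing-at-random basis is prior outcome and baseline covariates in the model. Distress arising during the waiting period is neither.

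**3. The plan's own power figure.** Inputs from Power Analysis: 80 and 40 randomized, 20% attrition (64 and 32 assessed), SD 50, rho 0.3, alpha 0.05 (taken as two-sided; sidedness is not stated).

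SE in SD units = sqrt[(1/64 + 1/32) × (1 − 0.3²)] = 0.2065. The detectable effect at 80% power is (1.96 + 0.842) × 0.2065 = 0.579 SD, or 28.9 units. This agrees with the stated 0.60 (30 units) on the table's 0.05 grid. Power at 0.60 is Phi(0.6/0.2065 − 1.96) = 82.8%.

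**4. Illustration of the shift.** The exit share q and the correlation r between distress and SDNN are assumptions; the documents give neither. Exits are taken as the most distressed controls and are counted inside the planned 20% attrition (2, 4 or 8 of 40).

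With lambda = phi(z at 1−q)/(1−q), the shift in SD units is r × (1 − rho) × lambda if distress correlates equally with baseline and week-7 SDNN. It is r × lambda if distress is unrelated to baseline SDNN.

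| q, r | lambda | Shift, equal correlation | Shift, no baseline correlation |
|---|---|---|---|
| 5%, 0.2 | 0.109 | 0.0152 SD = 0.8 ms | 0.0217 SD = 1.1 ms |
| 10%, 0.3 | 0.195 | 0.0409 SD = 2.0 ms | 0.0585 SD = 2.9 ms |
| 20%, 0.3 | 0.350 | 0.0735 SD = 3.7 ms | 0.105 SD = 5.2 ms |

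Power is Phi((0.6 ∓ shift)/0.2065 − 1.96). Two-sided type I error is Phi(−1.96 − shift/0.2065) + Phi(−1.96 + shift/0.2065). For the equal-correlation column:

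- Removed controls would have had lower SDNN: the effect is understated, and power is 80.8 / 77.2 / 72.2%.
- Removed controls would have had higher SDNN: the effect is overstated, and apparent power is 84.6 / 87.4 / 90.3%.
- Type I error in either direction: 5.1 / 5.5 / 6.5%.

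For the last column, power in the lower-SDNN case is 80.0 / 74.6 / 66.9% and type I error is 5.1 / 5.9 / 8.0%. If exit is unrelated to SDNN, the shift is zero and power stays at 82.8%.

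**5. The cost of retaining these controls.** Assume the other 8 planned control losses do not overlap with them as far as possible, so assessed controls number 32 + 40q = 34 / 36 / 40. The exits' share is then w = 40q/(32 + 40q) = 0.059 / 0.111 / 0.200. If all of them had the full 30 ms benefit by T2, the as-randomized contrast would be diluted by 30w = 1.8 / 3.3 / 6.0 ms.

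If exit is unrelated to SDNN, retention gains power only when these controls have reached less than about 34% of the full effect by T2.

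**The case against.** The strongest reply is that the plan is not silent. Analysis by randomized arm, maximum likelihood on all available data, multiple imputation and pattern-mixture models together supply a default: the person stays in WP-CON with a baseline value, and week 7 is missing. That stands. A reader might infer that the plan deletes these people from the intent-to-treat set, or that it has no way to analyse them. The documents support neither: no passage says that leaving the study means leaving the analysis, and the general rules apply unless something overrides them.

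The imputation model can also use more than the primary model does. It admits covariates predictive of missingness, so baseline PCL and HADS are available for every exit, two-weekly PCL scores for later ones, and possibly measures from the waitlist calls. This too stands, but these are sensitivity analyses. They reduce a bias without replacing the unmeasured week-7 value, and no distress-exit scenario is named.

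The exit rate may be close to zero, since exit needs both a call in distress and a wish not to wait for the CPT-C already on offer. The documents cannot exclude this. The 20% case needs all 8 planned control losses to be distress exits.

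Finally, CPT-C is used as a tool to create a contrast in symptoms, so declining to use the outcomes of treated controls is a defensible target. But the plan's stated intent-to-treat analysis ignores adherence, and nothing in the text says that the exit rule was chosen to serve a different target.

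**Conclusion.** The point holds as a cheap improvement of minor weight. A stated rule, confined to the smaller arm and driven by distress after randomization, forgoes outcomes that the plan elsewhere tries to keep. It needs to be reconciled with General Analytic Strategies, the Aim 2 analysis and Potential Difficulties.

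The size is not known. On assumed exits of 5 to 20% and correlations of 0.2 to 0.3, the shift is about 1 to 5 ms against 30 ms. It depends on how distress relates to baseline as well as week-7 SDNN, so the decimals should not be over-read.

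Two stronger conclusions are tempting. One is that the rule favours CPT-C, or works against it. The direction turns on whether removed controls would have had higher or lower SDNN, which the documents do not say. The other is that keeping these controls is bound to raise power or reduce error. That depends on how much therapy they have had by T2, which is also not given.

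**What to change.** Leave clinical care as it is. In the WP-CON section, state that these participants leave the waiting condition but are still invited to the scheduled T2 assessment, are analysed in their randomized arm, and have the exit reason and any therapy start date recorded. Carry the same statement into General Analytic Strategies, the Aim 2 dropout rule and Potential Difficulties, so that the four places agree. Report exits by arm and reason. Beside the as-randomized estimate, report a sensitivity estimate with values obtained after therapy began set to missing. Name distress exits in Missing Data and list the symptom scores to be used in the imputation model, which the current text already permits.

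The cost is protocol and SAP wording. T2 is already scheduled and paid in both arms. The downside is dilution of the as-randomized contrast if therapy starts before T2: up to about 1.8 / 3.3 / 6.0 ms at 5 / 10 / 20% exits, so a gain in power is not guaranteed. If the sponsor prefers not to seek T2 after such an exit, the plan should say so and define how these people enter each analysis.
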